2.4 RANDOMIZATION

A randomization list (1:1 experimental arm to controls), stratified by gender (IPF progression is gender-dependent), and use vs. non-use of antifibrotics (i.e., either pirfenidone or nintedanib) at enrollment, will be generated by the Data Coordinating Center (DCC) in advance. Given our "n", additional stratifications could result in imbalances with no subjects in certain cells.

The subject selection and randomizations, and specimen acquisitions for primary and secondary endpoint determinations (to follow), will also enable provision of blood specimens for the translational studies in other associated translational studies. Subject selections here will also identify a population from whom potential participants in additional studies (e.g., experimental bronchoscopies) can be approached and recruited. However, experimental bronchoscopies are optional and distinct from this clinical trial and will require an additional, separate IRB approval and signed consent. The subjects randomized to this GKT137831 clinical trial may elect to not participate with experimental bronchoscopy or other experimental procedures, and they will not be pressured to do so.

2.5 STUDY TREATMENT

The two arms of the study are:

- **Arm A (n=30) – GKT137831 Treatment:**

GKT137831 will be administered orally (p.o.), at doses of 400 mg, twice daily (bid), for a total of 24 weeks.

- **Arm B (n=30) - Placebo Treatment:**

Arm B subjects will be treated with otherwise identically-appearing placebo medication for the same duration.

Investigational pharmacies at each of the sites will be responsible for dispensing trial medications (either Arm A or Arm B), based on the randomization of that patient and transmission of that information by the DCC.

2.5.1 Description and formulation

Drug code	GKT137831	Placebo
Formulation	Micronized API formulated with excipients in capsules	Matching capsules containing only the excipients
Strength	100 mg	-
Route	Oral	Oral

GKT137831 capsules will contain 100 mg GKT137831 powder formulated with the following excipients per capsule: microcrystalline cellulose, Aerosil® (silicon dioxide), magnesium stearate and hard gelatin.

2.5.2 Packaging and labeling

The Investigational Medicinal Product (IMP) will be packed and labeled in accordance with applicable local regulatory requirements and applicable International Conference for Harmonization (ICH) Good Manufacturing Practice (GMP) and ICH Good Clinical Practice (GCP) guidelines, and to protect the blinded nature of this clinical study.

Child resistant 150 mL high-density polyethylene (HDPE) bottles with a tamper evident seal containing 70 capsules of either 100 mg GKT137831 capsules or matching placebo.

2.5.3 Storage and Stability

The IMP must be stored in a cool, dry, area at room temperature (between 15°C and 25°C). At the site IMP must be securely locked and stored with restricted access. Temperature should be controlled during shipment and during storage at study centers. The IMP must not be frozen or stored above 27°C.

2.5.4 Administration

The IMP will be orally self-administered BID, once in the morning and once in the evening (aiming for a period of at least 10 hours between doses) with meals or up to 30 minutes after a meal.

2.6 STUDY PROCEDURES AND MEASURES

Routine clinical care for IPF patients will be followed as ordered by the primary physician.

The study will log the results of specific screening-baseline measures, and other selected tests that may be obtained during the routine provision of clinical care and/or safety monitoring of trial participants. These may include: electrocardiograms (EKG), complete blood count (CBC), comprehensive metabolic panel (CMP) that includes electrolytes, glucose, BUN, and serum creatinine, pregnancy tests, thyroid function tests (TFT) consisting of thyroid stimulating hormone (TSH), thyroxine (T4), and liver function tests (LFT) consisting of albumin, total bilirubin, aspartate alanine transaminase (ALT), and aspartate glutamine transaminase (AST).

A maximum of thirty-four (34) ml of blood for experimental research studies and endpoint measures will be obtained pretreatment and at 6 week intervals throughout 24 weeks of drug therapy.

The following information will be collected and entered into the study case report forms (CRFs) and/or web-based data collection system. Clinical and laboratory data may include results of studies otherwise obtained for routine clinical care, which can be collected from medical records.

1. Physician names and contact information, general medical and surgical histories, co-morbidities, concurrent medications, and allergies.
2. Recording of vital signs, demographics, and medication regimen.
3. Review of medications
4. Brief assessment of symptoms.
5. Recording of laboratory and clinical testing results.

2.6.1 Variances

A variance of 5 days will be allowed for the telephone contacts to account for weekends or holidays. A variance of 10 days will be allowed for each outpatient follow-up visit for similar reasons, as well as potential logistic/transportation problems. If subjects are hospitalized at the time of scheduled assessments, an identical evaluation and procedures will be performed (as feasible):

The schedule for patient assessment and data collection is outlined as follows.

2.6.2 Screening

Screening (within 30 days prior to randomization):

Eligible patients will be evaluated by review and, if eligible, the study will be explained to them in detail, prior to their being asked to provide Informed Consent. Patients will undergo screening assessments to determine that inclusion/exclusion criteria are met prior to randomization and subsequent study drug treatments. The screening assessments may take place over >1 day.

The following tests and procedures will be performed after providing informed consent, but prior to randomization (see Table 1):

- Detailed medical history and demographics.
- Physical exam and inpatient progress assessment to include vital signs and blood pressure.
- Laboratory evaluations, not performed during routine clinical assessments and thus specific for Inclusion/Exclusion Criteria to include: EKG, CBC, CMP, TFT, LFT, blood pregnancy test (if applicable), FSH (if applicable)- see Section 5.7.3.1, and chest HRCT.

2.6.3 Initial experimental procedures

Day -30 to Day 1 (After Randomization, but Prior to Initiation of Therapy):

Randomization should occur as soon as possible after meeting confirmed eligibility, but within ≤ 30 days of their qualifying laboratory and other protocol-specific tests. Patients that meet all inclusion/exclusion criteria will be randomized to receive one of the study treatments described above in Section 2.5. In addition, the following data and specimens will be obtained (if not already obtained during screening):

- Physical exam and interval progress assessment to include vital signs and blood pressure.
- Venous blood by phlebotomy (a maximum of 34 ml) will be obtained, locally processed and stored frozen, for later batch shipment (frozen) to the Clinical Coordinating Center (CCC).
- Pulmonary function tests (PFTs) to include spirometry and diffusing capacity (DLCO).
- Six minute walk distance (6MWD). 6MWD = 0 among subjects unable to ambulate.
- Medication review
- Adverse Event (AE) assessment.

Day 1 (Initiation of Therapy):

- Subjects will receive study medication (>6 week supply), instructions, and drug compliance diary.
- Female subjects with childbearing potential (see Section 5.7.3.1) must have a negative urine pregnancy test prior to receiving study medication.

2.6.4 Follow-up monitoring (see Table 1 and Table 2)

Day 14 (2nd week):

- Telephone call (if outpatient, or personal visit if an inpatient) to assess status (brief assessment of symptoms, and a review of medical or surgical histories).
- AE assessment

Day 28 (4th week):

- Telephone call (if outpatient, or personal visit if an inpatient) to assess status (brief assessment of symptoms, and a review of medical or surgical histories).
- AE assessment

Day 42 (6th week):

- Physical exam and interval history assessment to include vital signs and blood pressure.
- Safety tests to include: EKG, CBC, CMP, TFT, LFT, pregnancy test, either urine or blood (if applicable).
- Venous blood by phlebotomy (a maximum of 34 ml) will be obtained, locally processed and stored frozen, for later batch shipment (while frozen) to the CCC.
- Medication review (including review of drug compliance diary)
- AE assessment.
- PK samples (2 ml each) taken upon arrival in clinic and just prior to departure from clinic

Day 56 (8th week):

- Telephone call (if outpatient, or personal visit if an inpatient) to assess status (brief assessment of symptoms, and a review of medical or surgical histories).
- AE assessment

Day 70 (10th week):

- Telephone call (if outpatient, or personal visit if an inpatient) to assess status (brief assessment of symptoms, and a review of medical or surgical histories).
- AE assessment

Day 84 (12th week):

- Physical exam and interval history assessment to include vital signs and blood pressure.
- Safety tests to include: EKG, CBC, CMP, TFT, LFT, pregnancy test, either urine or blood (if applicable),
- Venous blood by phlebotomy (a maximum of 34 ml) will be obtained, locally processed and stored frozen, for later batch shipment (while frozen) to the CCC.
- Medication review (including review of drug compliance diary)
- AE assessment.
- PK samples (2 ml) taken upon arrival in clinic and just prior to departure from clinic

Day 98 (14th week):

- Telephone call (if outpatient, or personal visit if an inpatient) to assess status (brief assessment of symptoms, and a review of medical or surgical histories).
- AE assessment

Day 112 (16th week):

- Telephone call (if outpatient, or personal visit if an inpatient) to assess status (brief assessment of symptoms, and a review of medical or surgical histories).
- AE assessment

Day 126 (18th week):

- Physical exam and interval history assessment to include vital signs and blood pressure.
- Safety tests to include: EKG, CBC, CMP, TFT, LFT, pregnancy test, either urine or blood (if applicable),
- Venous blood by phlebotomy (a maximum of 34 ml) will be obtained, locally processed and stored frozen, for later batch shipment (while frozen) to the CCC.
- Medication review (including review of drug compliance diary)
- AE assessment.

Day 140 (20th week):

- Telephone call (if outpatient, or personal visit if an inpatient) to assess status (brief assessment of symptoms, and a review of medical or surgical histories).
- AE assessment

Day 154 (22nd week):

- Telephone call (if outpatient, or personal visit if an inpatient) to assess status (brief assessment of symptoms, and a review of medical or surgical histories).
- AE assessment

Day 168 (24th week):

- Physical exam and interval history assessment to include vital signs and blood pressure.
- Safety tests to include: EKG, CBC, CMP, TFT, LFT, pregnancy test, either urine or blood (if applicable),
- Venous blood by phlebotomy (a maximum of 34 ml) will be obtained, locally processed and stored frozen, for later batch shipment (while frozen) to the CCC.

- Pulmonary function tests (PFTs) to include spirometry and diffusing capacity (DLCO).
- Six minute walk distance (6MWD). 6MWD = 0 among subjects unable to ambulate.
- Chest HRCT
- Medication review (including review of drug compliance diary)
- AE assessment.

Day 198 (28th week):

- Telephone call (if outpatient, or personal visit if an inpatient) to assess status (brief assessment of symptoms, and a review of medical or surgical histories).
- AE assessment

Every effort will be made to ascertain status among those seemingly lost to follow up by contacting patient or next of kin, conducting internet searches for obituaries, etc.

Table 1. TREATMENT PROCEDURE SCHEMATIC

The experimental interventions are outlined below:

Weeks:	-4 to 0	0	6	12	18	24
Clinic Visit	x	x	x	x	x	x
Randomization		x				
Exam and Interval History	x	x	x	x	x	x
Dispense Drug		x	x	x	x	
Review Drug Diary			x	x	x	x
Safety Assessment*	x	x	x	x	x	x
Blood Pregnancy Test	x					
HRCT		x				x
Spiro and DLCO		x				x
6MWD		x				x
PK Sampling			x	x		
K-BILD QOL Survey	x					x
Urine Pregnancy**		x	x	x	x	x

*Safety assessments include electrocardiogram (EKG), complete blood count (CBC) with platelets (plts), basic metabolic panel (BMP) with glucose, BUN, creatinine, blood pregnancy test, if applicable (Section 5.7.3.1), liver function tests (LFT) with albumin, bilirubin (total), transaminases, and thyroid function tests (TFT) with thyroid stimulating hormone (TSH) and thyroxine (T4). These assessments can be combined during screening and baseline visits as long as they are completed within 30 days of randomization and start of drug treatment. ** if applicable (see Section 5.7.3.1). In addition to the blood pregnancy test during screening, a urine (or blood) pregnancy test must be performed on the day that therapy starts. Blood tests can also substitute for urine tests at weeks, 6,12,18,24.

Table 2. PHONE CONTACTS

Weeks:	2	4	8	10	14	16	20	22	28
Phone contact	x	x	x	x	x	x	x	x	x

Subjects will be contacted by the study coordinators at these times to assess for symptoms potentially related to adverse effects of medications, review of medication changes, and interval medical or surgical histories including emergency or physician office visits.

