1.3.12. Summary of Clinical Studies with GKT137831

Healthy Subjects Program

Four Phase 1 studies were conducted with GKT137831 in order, in part, to characterize the safety and tolerability profile of GKT137831 in healthy male subjects. The studies were designed to examine the safety and pharmacokinetics of single and multiple ascending doses of GKT137831, the potential for drug interactions through the inhibition of CYP3A4 substrate midazolam, as well as the relative bioavailability of micronized and unmicronized GKT137831 and the potential interactions with food.

A total of one hundred and five (105) healthy male subjects received GKT137831 in four Phase 1 studies. All the Phase 1 studies were conducted at a single clinical pharmacology unit located in Paris, France and were all conducted in accordance with the principles of Good Clinical Practice (GCP). Doses administered ranged between 10 mg and 1800 mg. In the multiple dose study, GKT137831 was administered over 10 successive days. The mean age of subjects in all four studies was between 30.0 and 33.6 years (mean) with a range of 18 to 49 years.

In the phase I program, GKT137831 was well tolerated with low incidence of adverse events. There were no deaths, no serious adverse events, and no adverse event of severe intensity. Most were treatment emergent adverse events (TEAEs) and were mild and self-limiting, and were considered not related to treatment by the Investigator. Of the 105 subjects dosed with GKT137831 or matching placebo in the 4 Phase 1 studies, 41 subjects reported adverse events (39%), of which 39 were TEAEs. The most frequently reported TEAEs in subjects receiving GKT137831 were events related to headaches (10 TEAEs i.e. 25.6%). Other TEAEs were non-specific infections unrelated to GKT137831.

There were no vital sign, ECG, hematology, clinical chemistry or urinalysis findings of any clinical significance, as defined by the principal investigator. Thyroid hormones were investigated in the multiple ascending dose study and all mean values were within the normal range and changes compared to baseline showed no trend over time.

The pharmacokinetics of GKT137831 were generally consistent between all four studies. Administration of micronized rather than unmicronized drug substance did not appear to have any notable impact on plasma exposure. Administration with food did have an impact on extent of exposure and/or inter-subject variability.

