2.6.5 Specimen Collection and Management

Specimen Collection / Documentation: A maximum of 34 ml of blood for experimental research studies and endpoint assays will be obtained pretreatment, and at weeks 6, 12, 18, and 24 after the start of therapy. The peripheral blood will be processed at the site of collection by centrifugation to separate mononuclear cells, plasma, and sera, which will be aliquoted and frozen (at -20° or below) until shipment to the CCC in batches. Subsequent assays will be conducted in the laboratory of CCC investigators or their colleagues, in compliance with IRB approvals.

Each research sample will be labeled with the subject's unique identifier, sample date, and sample collection time. The code number and date on which the specimen is frozen, all other information about the specimen, and subsequent processing will be entered on a specimen processing worksheet.

Covariate information, e.g., concomitant medications, laboratory values, etc., will be obtained at each time point.

Specimen Handling and Labeling (De-Identification)

All research specimens and all records associated with the samples will be labeled only with a unique code that links to the trial data, but contains no personal identifiers. The information linking these code numbers to the corresponding subject's identity will be kept in a secure location in the PI's office at each participating center, and will not be available to staff managing samples at the research laboratories.

Specimen Management and Storage: Specimens in excess of immediate assay requirements may be stored indefinitely in a secured freezer under the control of the responsible PI. The coding information linking patient identifiers to the stored samples will be maintained in a locked, secure area that will be accessible only to the study investigator. Subjects may request to have their samples destroyed at any time. These samples will be destroyed immediately upon receipt of the subjects' written request to do so.

Restrictions to Direct Access of Specimens: Specimens will be kept in the responsible study investigators' laboratories indefinitely and will be under the control of the PI. Other personnel not involved with the management or operations of the study are not permitted direct access to the specimens.

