b) and c) FVC and 6MWD: This is a Phase IIb study and is likely underpowered for rigorous evaluation of drug effects on clinical endpoints, such as FVC changes and/or 6MWD over time. Nonetheless, measures and comparisons of these parameters will enable us to detect striking drug efficacy, and will likely be informative with respect to power calculations for later, more definitive efficacy trials. FVC is a measure of pulmonary restriction (in turn, a function of the underlying lung fibrosis). 6MWD are simple, inexpensive, reproducible measures of global cardiopulmonary function. Values for 6MWD can be obtained in all patients, even those who are immobile (e.g., value = 0). Measures of FVC and 6MWD will be performed per ATS/ERS guidelines. These tests are standard of practice (SOP) in our IPF clinics.

2.7.3. Safety Endpoints:

Adverse events: Adverse events (AE) that occur anytime during participation in this study will be recorded and compared. The NCI Common Toxicity Criteria Scale will be used to define grades (severity) of adverse events and toxicities. An AE is defined as any untoward medical occurrence in a subject, regardless of its relationship to these treatments. Toxicity is an adverse event with a direct relationship to the study drug. All toxicities are AE, but not all AE are toxicities. Computer data entry (and case report forms- [CRF]) will require responses to all adverse events, with a particular focus on infections (including location and organism), and metabolic perturbations (e.g., cardiac, liver, bone marrow, or thyroid abnormalities) hyperglycemia, hypotension, etc.). Recording all AEs in pre-specified checklists (and free text entries), will guard against unintended bias in this unblinded trial. We hypothesize GKT137831 will be safe in this population, and will not be associated with an increased number or severity of AE in comparison to placebo.

2.7.4. Pharmacokinetic endpoints:

Plasma concentrations of GKT137831 and its main phase 1 metabolite, GKT138184. The plasma concentrations will be subjected to population PK analysis to estimate population PK parameters such as clearance and volume of distribution and associated inter-individual variability (IIV), and to determine predictors of IIV. PK-PD analysis will be carried out using the primary endpoint and selected secondary endpoints in order to explore any potential PK- PD relationships.

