2.8.4 Pharmacokinetics Analyses

Plasma concentrations of GKT137831 and its main phase 1 metabolite, GKT138184 will be analyzed in plasma specimens obtained at weeks 6 and 12 of the drug therapy. The plasma concentrations will be subjected to population PK analysis to estimate population PK parameters such as clearance and volume of distribution and associated inter-individual variability (IIV), and to determine predictors of IIV. The sparse PK data from this study will be integrated into a population PK model using nonlinear mixed-effects modeling. In addition, PK-PD analysis will be carried out using the primary endpoint and selected secondary endpoints in order to explore any potential PK- PD relationships.

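### PK sampling follows clinic arrival and departure rather than the dose, so between-patient variability in V/F may be estimated far less precisely than the same four samples allow

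*Combined protocol and SAP*

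**What the plan says.** Section 2.6.4 ties PK sampling to the clinic visit. Day 42 has "PK samples (2 ml each) taken upon arrival in clinic and just prior to departure from clinic" and Day 84 has "PK samples (2 ml) taken upon arrival in clinic and just prior to departure from clinic". Section 2.8.4 confirms that drug and metabolite "will be analyzed in plasma specimens obtained at weeks 6 and 12 of the drug therapy", so each patient gives at most four samples. Section 2.5 puts 30 patients on active drug.

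Section 2.7.4 says that the concentrations will be used to "estimate population PK parameters such as clearance and volume of distribution and associated inter-individual variability (IIV), and to determine predictors of IIV", with an exploratory PK-PD analysis to follow. Section 2.8.4 repeats this, calls the data sparse, and plans to integrate them into a nonlinear mixed-effects population model. It names no source model, prior data or fixed parameters.

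On timing, Section 2.6.5 has each research sample labelled with "sample date, and sample collection time". Section 2.5.4 states "The IMP will be orally self-administered BID, once in the morning and once in the evening", at or shortly after a meal, aiming for at least 10 hours between doses. Section 1.3.12 reports that "Administration with food did have an impact on extent of exposure and/or inter-subject variability". An adherence diary is issued on Day 1 and reviewed at both PK visits, but its fields are not described and no section links it to PK. Nothing says where the morning dose falls relative to arrival on a PK day.

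**The concern.** A concentration informs a PK model only when it can be placed on the dosing interval, which needs time since dose as well as clock time. Clock time is secured. Dose time is left to a diary whose content is unknown. An unrecognised difference in dose or meal time would be read partly as between-patient variability, which is one of the promised outputs.

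The second issue is spread. Volume is learned from the shape of the curve, by comparing early with late concentrations. Two visits under the same instruction may sample the same stretch for a given patient, and nothing in the plan steers them apart. At stake are the between-patient variance of V/F and the search for its predictors. The primary endpoint is not touched.

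**Working it through.** The plan gives no PK precision figure, so there is none to reproduce. I calculated the expected precision instead.

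**Inputs from the documents.** 30 active patients; 400 mg every 12 h; two samples at each of two visits, so 30 × 4 = 120 samples at most. Section 1.3.12 gives a mean AUC of 24,100 to 38,000 ng·h/mL after 300 mg, so CL/F is between 300 mg ÷ 38.0 mg·h/L = 7.9 L/h and 300 ÷ 24.1 = 12.4 L/h. I used 10 L/h. With error on the log scale, only the half-life affects the results below.

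**Assumptions (not in the documents).** One compartment; half-life 4, 6 or 8 h; ka fixed at 1/h; between-patient SD ω = 0.4 for CL and V on the log scale; residual SD σ = 0.2; dose times known.

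**Model.** With k = CL/V and τ = 12 h, at steady state

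C(t) = D·ka / [V(ka − k)] × { e^(−kt)/(1 − e^(−kτ)) − e^(−ka·t)/(1 − e^(−ka·τ)) }.

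Let J hold the derivatives of log C with respect to log CL and log V, and W = ω²JJᵀ + σ²I. The information is n·JᵀW⁻¹J for the typical values and n·½tr(W⁻¹ ∂W W⁻¹ ∂W) for the variances, with the residual variance estimated. One patient's posterior covariance is (JᵀJ/σ² + I/ω²)⁻¹.

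**Why spread matters.** At a 6 h half-life, the derivative of log C with respect to log V is −0.34, −0.19, +0.26 and +0.49 at 2, 4, 8 and 10 h. Samples at 2 and 4 h span 0.15 of this scale; adding 8 and 10 h spans 0.83.

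**Results, in % (half-life 4 / 6 / 8 h).**

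| Sample times | RSE CL/F | RSE V/F | RSE of variance of V/F | Individual V: posterior SD as % of prior |
|---|---|---|---|---|
| 2, 4 h at both visits | 9 / 10 / 11 | 13 / 19 / 29 | 69 / 137 / 258 | 78 / 89 / 94 |
| Arrival varies over 1-6 h, stay 2-4 h | about 8 | 10 / 12 / 15 | 50 / 77 / 115 | not needed here |
| 2, 4 h at one visit; 8, 10 h at the other | about 8 | 9 / 10 / 11 | 37 / 45 / 59 | 53 / 64 / 73 |

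An RSE above 50% puts the estimate within two standard errors of zero. At a 6 h half-life the true variance is 0.4² = 0.16. Its standard error is 0.16 × 1.37 = 0.22 with repeated times and 0.16 × 0.45 = 0.07 with separated times.

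**Other assumptions.** A second calculation used half-lives of 3, 6 and 12 h, ka of 0.5 or 1.5/h with 60% between-patient SD, and residual error 25%. With arrival 2-4 h after dose and a 2-3 h stay at both visits, the RSE of the variance of V/F is 63-1974%, or 63-1382% with ka fixed. Four samples spread over the interval give 35-245%. Typical V/F is 12-182% (11-67% with ka fixed), against 9-35% when spread. CL/F is 13-16% with ka estimated and 8-10% with ka fixed.

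**Dose-time error.** After the peak, a 2 h error changes the expected concentration by a factor 2^(2/half-life): 1.41, 1.26 and 1.19. Against an assumed residual error of 20% this is larger at 4 and 6 h and about equal at 8 h. The 2 h is itself an assumption.

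**The case against.** **Dose and meal times may be recorded.** A reader might infer that they are not collected. The documents do not support that. Sample time is on the label, the diary is reviewed at both PK visits, and Section 4.1.2 adds pill counts and a verbal medication review. The diary and CRF fields are simply not shown. What stands is that capture for PK is not specified.

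**The repeated pattern is assumed.** The same instruction does not mean the same hours: no clinic times, lengths of stay or dose position on PK days are stated, and five centers may differ. The 2 and 4 h case is unfavourable by construction. With varied arrivals most of the loss in typical V/F disappears (10-15% against 9-11%). A gap remains for the variance (50-115% against 37-59%), and the plan leaves that spread to chance.

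**V/F is not lost.** A reader might infer that volume cannot be estimated. In the main calculation typical V/F has an RSE of 13-29% even in the unfavourable case, which is moderate for an exploratory aim. CL/F, which determines average exposure and so matters most for PK-PD, is little affected.

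**Earlier data could help.** Section 2.8.4 speaks of integration into a population model, and Section 1.3.12 describes four Phase 1 studies with PK data. Borrowing could reduce the loss, and fixing ka above already presumes some. In the second calculation, fixing ka helped typical V/F much more than the variance of V/F.

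**Sample size is also a limit.** This stands. With 30 patients and four samples each, separated visits still leave the variance of V/F at 37-59%, and worse under harder assumptions.

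**Conclusion.** The concern holds in a limited form. PK sampling has no dose-relative spread, and dose and meal timing for PK is unspecified. The output at risk is the between-patient variance of V/F and hence the search for its predictors. If a patient's two visits fall at similar times after the dose, separating them would cut that RSE by roughly half at a 4 h half-life (69% to 37%) and by about three quarters at 8 h (258% to 59%), with no extra blood. If arrivals already vary, the gain is smaller.

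These sizes rest on an assumed half-life, absorption rate, variability and arrival pattern, and on dose times being known. Bias from wrong dose times is not included. The change is worth making because it is cheap and because dose times missed at the visit are hard to recover later. It has no bearing on the primary analysis.

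**What to change.** - **Section 2.6.4:** book one of the Week 6 and Week 12 visits early and the other late in the interval between the morning and evening doses, leaving dosing as it is. The 8 and 10 h times above serve to size the gain; they need not become fixed windows.
- **PK form:** record the clock times of the last two doses before each sample, and whether and when the associated meal was taken. If the diary already holds these, say so and link it to the PK data.
- **Section 2.8.4:** describe results on predictors of variability in V as exploratory. If earlier PK data or fixed parameters will be used, name them.

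The cost is slightly less flexible booking for one visit and a few CRF fields. Samples, visits and assays stay the same.
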